9.4. Discontinuation of Study Treatment

Discontinuation of study treatment will be required if deemed by the investigator to be in the subject's best interest or if subject meets any of the criteria for study withdrawal listed below:

- Disease progression as assessed by RECIST 1.1 criteria (Appendix 1), unless the subject meets criteria for treatment beyond progression (Section 9.7);
- Termination of the study by Vanderbilt or relevant regulatory authority;
- Drug availability or study supply discontinued;
- The patient withdraws consent to undergo further treatment;
- The patient is lost to follow-up, refuses further follow-up, or is noncompliant;
- The patient no longer requires treatment (e.g. patients having experienced a tumor reduction followed by resection and no longer with evaluable disease);
- Initiation of treatment with another anti-cancer therapy;
- Additional protocol specified reason for discontinuation (e.g. related to adverse event), see Section 11.

In the case of pregnancy, the investigator must immediately notify the EMD Serono medical designee of this event. In most cases, the study drug will be permanently discontinued in an appropriate manner. If the investigator determines a possible favorable benefit/risk ratio warrants continuation of study drug, a discussion between the investigator and appropriate internal and external entities must occur (e.g. the IRB and the EMD Serono medical designee).

If a patient does not return for a scheduled visit, every reasonable effort should be made to contact the patient. In any circumstance, every reasonable effort should be made to document subject outcome, if possible. The investigator should inquire about the reason for withdrawal, request the patient to return for a final visit, if applicable, and follow-up with the patient regarding any unresolved treatment-related adverse events.

All subjects who discontinue study drug should comply with protocol specified follow-up procedures as outlined in Section 7. The only exception to this requirement is when a subject withdraws consent for all study procedures including post-treatment study follow-up or loses the ability to consent freely (e.g. is imprisoned or involuntarily incarcerated for the treatment of either a psychiatric or physical illness).

If study drug is discontinued, the reason for the discontinuation must be documented in the subject's medical records and entered on the appropriate CRF page.

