New lesions are considered measurable at the time of initial progression if the longest diameter is at least 10 mm (except for pathological lymph nodes, which must have a short axis of at least 15 mm). Any new lesion considered non-measurable at the time of initial progression may become measurable and therefore be included in the tumor burden measurement if the longest diameter increases to at least 10 mm (except for pathological lymph nodes, which must have an increase in short axis to at least 15 mm).

Upon documentation of further disease progression, avelumab treatment should be discontinued permanently. However, according to the investigator's clinical judgment and after any necessary discussion between the investigator and EMD Serono, if a patient with evidence of PD is still experiencing clinical benefit, the patient may be eligible for continued treatment with avelumab. The investigator's judgment should be based on the overall benefit-risk assessment and the patient's clinical condition, including performance status, clinical symptoms, adverse events and laboratory data.

Patients who stop avelumab treatment and then experience radiologic disease progression thereafter will be eligible for re-treatment with avelumab at the discretion of the investigator and after IRB approval and any necessary discussion with EMD Serono if: 1) no anti-cancer treatment was administered since the last dose of avelumab, 2) the patient does not meet the safety withdrawal criteria, and 3) the trial is still open. Patients will resume avelumab therapy at the same dose and schedule applied at the time of discontinuation.

Global deterioration of health status requiring discontinuation of treatment without contemporaneous evidence of objective disease progression should be reported as 'symptomatic

deterioration'. Every effort should be made to document objective progression (i.e. radiographic confirmation) even after discontinuation of treatment.

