10.2. Prohibited and/or Restricted Medications and Therapies

Patients are prohibited from receiving the following therapies during the treatment phase of this trial:

- Immunotherapy or immunosuppressive drugs (i.e. chemotherapy or systemic corticosteroids) except for short-term treatment of allergic reactions or for the treatment of an immune-related adverse event (irAE). Short-term administration of systemic steroids (e.g. for allergic reactions or the management of irAEs) is allowed. Topical and inhaled steroids are allowed.
- Systemic corticosteroids > 10 mg daily prednisone equivalent, except as stated in Section 10.1 or to treat a drug-related AE (e.g. Section 11).
- Growth factors (granulocyte colony-stimulating factor or granulocyte-macrophage colony stimulating factor) are prohibited.
- Vaccination within 28 days of the first dose of avelumab and while on study is prohibited, except for administration of inactivated vaccines (for example, inactivated influenza vaccines).
- Bisphosphonate or denosumab treatment is not allowed unless it has been initiated more than 14 days prior to receiving the first administration of avelumab.
- Anti-cancer systemic chemotherapy or biological therapy or investigational agents other than avelumab.
- Surgical resection of tumor.
- Other experimental pharmaceutical products.
- Herbal remedies reasonably known to have immunostimulating properties (e.g. mistletoe extract) or reasonably known to potentially interfere with major organ function (e.g. hypericin).

There are no prohibited therapies during the Post-Treatment Follow-up Phase.

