11. ADVERSE EVENT MANAGEMENT

11.1. Criteria for Holding Treatment for Adverse Event Possibly Related to Avelumab

No dose *reductions* of avelumab are permitted for the management of adverse events experienced by individual patients in this study.

As outlined below, *treatment delays* of up to 4 weeks (28 days) from last dose of avelumab are allowed.

Avelumab Treatment Should be DELAYED up to 4 Weeks (28 days) for the following Adverse Events if at least Possibly related to Avelumab:

- Any Grade \geq 3 drug-related adverse event, with the exception of alopecia and the following laboratory exceptions for lymphopenia, leukopenia, AST, ALT, and total bilirubin:
 - Grade 3 lymphopenia or leukopenia do not require a dose delay.
 - If subject had baseline AST, ALT, or total bilirubin within normal limits, then delay dosing for drug-related Grade \geq 2 liver function toxicity.
 - If subject had baseline AST, ALT, or total bilirubin that was Grade 1, then delay dosing for drug-related Grade \geq 3 liver function toxicity.
- Any AE, laboratory abnormality, or intercurrent illness regardless of severity or attribution to avelumab which, in the judgment of the investigator, warrants delaying investigational treatment with avelumab.

IMPORTANT:

The above list does NOT include other events which may require holding study treatment – even in cases of severity less than Grade 3 and regardless of attribution to study drug. Events such as Immune-Related Adverse Events (irAEs) of Special Interest, Infusion Reactions, Hypersensitivity, or Tumor Lysis Syndrome (if applicable) should be managed according to local institutional practice.

Dose delay criteria apply for drug-related adverse events – i.e. events which in the investigator's opinion are possibly, probably, or definitely related to avelumab. For adverse events deemed unlikely or unrelated to avelumab (e.g. related to disease), the medical judgement of the investigator should determine the extent to which a treatment delay is appropriate.

If avelumab treatment is delayed for > 4 weeks (28 days) from the last dose of avelumab, the subject must be permanently discontinued from study therapy, except as may be specified in Sections 9.4 and 11.3.

The window for a maximal 4 week (28 day) avelumab treatment delay begins on the calendar day of the most recent avelumab treatment preceding an event in question, and concludes on the calendar day that an immediately subsequent avelumab treatment is initiated.

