11.2. Criteria for Resuming Treatment Held for Adverse Event Related to Avelumab

If a subject's avelumab treatment is held due to an adverse event that is possibly, probably or definitely related to avelumab, the subject may resume treatment with avelumab when the related adverse event resolves to \leq Grade 1 or to patient's baseline value, with the following exceptions:

- Subjects may resume treatment in the presence of Grade 2 fatigue or alopecia of any grade.
- Subjects who have not experienced a Grade 3 drug-related skin AE may resume treatment in the presence of Grade 2 skin toxicity
- Subjects with a Grade 2 AST/ALT or total bilirubin may resume treatment IF patient's respective baseline AST/ALT or total bilirubin was Grade 1 and the reason for patient's dose delay was NOT due to a 2 or more grade increase in AST/ALT or total bilirubin.
- Subjects with combined Grade 2 AST/ALT AND total bilirubin values meeting discontinuation parameters should have treatment permanently discontinued
- Drug-related pulmonary toxicity or colitis must have resolved to baseline before treatment is resumed
- Drug-related endocrinopathies adequately controlled with only physiologic hormone replacement may resume treatment.

The subject's baseline value is defined as the most recent value preceding initiation of the patient's first dose of avelumab.

In the event study treatment is held due to an event the investigator feels is unlikely related or not related to avelumab (e.g. hold study drug per investigator discretion in order to evaluate appropriate attribution to disease versus drug), then resumption of avelumab may proceed according to the medical judgement of the investigator (with maintained accordance to other protocol sections).

If treatment is delayed > 4 weeks (28 days) from the last dose of avelumab, the subject must be permanently discontinued from study therapy, except as may be specified in Sections 9.4, 11.2 and 11.7.

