14.5.12 Adverse Events of Special Interest (AESIs)

Any adverse event that is suspected to be a potential immune-related adverse event (irAE) is considered an AE of special interest (AESI). Specific guidance for the management of irAEs is provided in Section 11.7. AESIs are reported according to the general AE reporting rules specified in Section 14.5.

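### Sections 11.1 and 11.2 stop avelumab for good once more than 28 days pass between doses, but five immune-event rows in 11.6 allow a restart only after a steroid taper of at least a month

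*Combined protocol and SAP*

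**What the plan says.** Section 11.1 allows treatment delays of up to 28 days. Beyond that, "the subject must be permanently discontinued from study therapy, except as may be specified in Sections 9.4 and 11.3". The window "begins on the calendar day of the most recent avelumab treatment preceding an event in question" and closes on the day of the next infusion, so a restart on day 28 is still allowed.

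Section 11.2 repeats the limit with a different list of exceptions: "the subject must be permanently discontinued from study therapy, except as may be specified in Sections 9.4, 11.2 and 11.7". Its general test for restarting is by grade: "the subject may resume treatment with avelumab when the related adverse event resolves to" Grade 1 or lower, or to baseline (baseline is required for colitis and pulmonary toxicity). It sets no condition on steroids.

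In Section 11.6, five rows withhold avelumab, give steroids, taper them over a month or more and only then resume:
- initial Grade 3 diarrhea/colitis
- initial Grade 3 rash
- Grade 2 pneumonitis
- Grade 2-3 renal events
- Grade 2 or first Grade 3 irAE of another kind

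Persistent or recurrent Grade 1-2 rash follows the same path if steroids are used; that row only asks that they be considered.

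**The concern.** For the same recovered patient, 11.6 says to resume after the taper, while 11.1, read literally, says to stop permanently. A patient stopped under 11.1 has only a narrow way back. Section 9.7 reads "Patients who stop avelumab treatment and then experience radiologic disease progression thereafter will be eligible for re-treatment", so a patient whose disease is still controlled does not qualify, and 9.7 also excludes anyone who meets the safety withdrawal criteria.

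The deadline also pushes in an unwelcome direction. An investigator who wants to keep a benefiting patient on drug has a reason to re-dose by day 28, before the taper is finished, and the grade-based test in 11.2 makes that arguable. What is at stake is which patients may be re-dosed after an immune toxicity, and whether they are still on steroids when it happens.

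**Working it through.** **Step 1: the day count.** The protocol states no figure for this interval, so there is none to reproduce. The gap from last dose to restart is

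gap = day of onset + days to Grade 1 or lower + length of taper,

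to be compared with 28. The limit and the way it is counted come from 11.1; the taper of at least a month comes from 11.6. The protocol does not define a month, so I take 28 to 31 days. Onset and recovery times are assumed.

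- Onset and recovery on the infusion day, 28-day taper: 0 + 0 + 28 = 28, just allowed.
- The same with a 30-day taper: 0 + 0 + 30 = 30, over.
- Onset day 1, recovery in 1 day: 1 + 1 + 28 = 30, over.
- Onset day 7, recovery in 5 days: 28 - 7 - 5 = 16 days left for a taper of at least 28.
- Grade 2 pneumonitis, onset day 7, using the 2 weeks that row allows for improvement: 28 - 7 - 14 = 7 days left.
- Onset day 14, recovery in 14 days, 31-day taper: 14 + 14 + 31 = 59.

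The limit is met only in the first, degenerate case.

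**Step 2: do the exceptions help?**
- Section 9.4, cited in both places, lists reasons to discontinue. For adverse events it only points back: "Additional protocol specified reason for discontinuation (e.g. related to adverse event), see Section 11".
- Section 11.3, cited in 11.1, covers infusion reactions and extends no hold.
- Section 11.2 also cites itself and 11.7. Section 11 ends at 11.6, in the contents list and in the text. Section 14.5.12 shows what 11.7 was meant to be: "Specific guidance for the management of irAEs is provided in Section 11.7". Reading 11.7 as 11.6 repairs 11.2 and leaves 11.1 in conflict.

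**Step 3: does 11.6 expect longer holds?** Its table for other irAEs stops treatment for a Grade 2 or 3 event only once it has persisted for 12 weeks, which is 12 x 7 = 84 days. Under a 28-day stop, an event that is being held could never reach that rule.

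**Step 4: is a mid-taper restart open?** Section 11.2 tests grade only. Section 10.2 bars systemic steroids above 10 mg prednisone equivalent a day "except as stated in Section 10.1 or to treat a drug-related AE", so it does not block dosing during an irAE taper. Section 10.3, however, permits therapeutic steroids for irAEs on the terms set in Section 11. A restart before the taper ends is therefore arguable, not clearly allowed.

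**Step 5: how often?** Section 4.5 gives Grade 3 or higher treatment-related colitis in 2 of 717 patients (this may include Grade 4). 2/717 = 0.00279; 25 x 0.00279 = 0.07 expected cases; 1 - (1 - 0.00279)^25 = 0.067, a 6.7% chance of at least one. I found no rate in the documents for Grade 2 pneumonitis, Grade 2-3 renal events or persistent Grade 2 diarrhea, so the total is unknown.

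**The case against.** The best reply is that the specific rule governs the general one. A note in 11.1 sets irAEs outside its hold list and leaves them to the practice of the site. The opening of 11.6 says irAEs are to be handled by that section unless the investigator judges another standard more suitable. With 11.2's evident intention and 14.5.12, this suggests that 11.6 was meant to control, and that the fault is one stale cross-reference and one missing one. As an account of intent this stands. But neither text lifts the 28-day limit, which is mandatory and names its own exceptions.

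Section 11.1 also says that a mid-cycle toxicity resolved by dosing day generally needs no delay. That could cover the patient with onset on day 7 who recovers by day 12. It does not remove the taper that 11.6 requires; it adds to the uncertainty.

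Four stronger readings are tempting and are not supported:
- *A mid-taper restart breaches 11.6 and nothing else.* Section 10.3 ties therapeutic steroids to Section 11, and the permissive wording of 11.2 need not override a specific row.
- *Grade 2 diarrhea/colitis that persists can never fit.* If it is then handled as an initial Grade 3 event, the gap is at least 5 + 28 = 33 days and up to 7 + 31 = 38 with no further recovery time. But the row says to treat it as Grade 3 or 4. Grade 4 is a permanent stop, resumption is limited to initial Grade 3, and the protocol does not say which applies.
- *The response rate is affected.* Nothing shows this. Scans continue until progression in patients who stop for other reasons (7.1, note 19).
- *The 12-week rules imply an 84-day cap on all irAE holds.* Those rules concern steroid need and persistence of the event, not the gap between doses. A cap would conflict with 11.6 again: an event resolving at 10 weeks gives 70 + 28 = 98 days.

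**Conclusion.** The point holds as a conflict in an operative dosing rule and should be corrected. Practically every patient managed by the five rows, or by the sixth when steroids are used, passes the 28-day limit before 11.6 lets avelumab restart. The excess runs from a few days to about a month in the examples (59 - 28 = 31 days in the longest). The irAE exemption that 11.2 very likely intends rests on a section that does not exist, and 11.1 has none.

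This assumes that a month means 28 to 31 days and that the 11.6 rows are followed as written; an investigator who uses a different local standard with a shorter taper could stay within the limit. The number of patients affected is unknown and may be small in a trial of 25. No effect on the response rate or on a planned safety endpoint is claimed.

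**What to change.** One amendment, with three corrected references and two added sentences:
- Add Section 11.6 to the exceptions in 11.1.
- Change 11.7 to 11.6 in 11.2 and in 14.5.12.
- State in 11.1 that a hold for an irAE managed under 11.6, together with any steroid taper required there, does not count against the 28-day limit.
- State in 11.2 that where an 11.6 row calls for a taper, avelumab restarts only when the taper is complete.

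Keep the 28-day limit for non-immune events. Leave the permanent-stop rows and the existing 12-week rules in 11.6 as they are. Whether to set an outer limit on irAE holds is a clinical choice for the sponsor.

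The change adds no visits or scans, since 9.2 and 11.1 already continue them during holds. The trade-off is that some patients are rechallenged after longer holds, which 11.6 already intends.

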11.2. Criteria for Resuming Treatment Held for Adverse Event Related to Avelumab

If a subject's avelumab treatment is held due to an adverse event that is possibly, probably or definitely related to avelumab, the subject may resume treatment with avelumab when the related adverse event resolves to \leq Grade 1 or to patient's baseline value, with the following exceptions:

- Subjects may resume treatment in the presence of Grade 2 fatigue or alopecia of any grade.
- Subjects who have not experienced a Grade 3 drug-related skin AE may resume treatment in the presence of Grade 2 skin toxicity
- Subjects with a Grade 2 AST/ALT or total bilirubin may resume treatment IF patient's respective baseline AST/ALT or total bilirubin was Grade 1 and the reason for patient's dose delay was NOT due to a 2 or more grade increase in AST/ALT or total bilirubin.
- Subjects with combined Grade 2 AST/ALT AND total bilirubin values meeting discontinuation parameters should have treatment permanently discontinued
- Drug-related pulmonary toxicity or colitis must have resolved to baseline before treatment is resumed
- Drug-related endocrinopathies adequately controlled with only physiologic hormone replacement may resume treatment.

The subject's baseline value is defined as the most recent value preceding initiation of the patient's first dose of avelumab.

In the event study treatment is held due to an event the investigator feels is unlikely related or not related to avelumab (e.g. hold study drug per investigator discretion in order to evaluate appropriate attribution to disease versus drug), then resumption of avelumab may proceed according to the medical judgement of the investigator (with maintained accordance to other protocol sections).

If treatment is delayed > 4 weeks (28 days) from the last dose of avelumab, the subject must be permanently discontinued from study therapy, except as may be specified in Sections 9.4, 11.2 and 11.7.

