
Grade 1 to 2 Covering ≤ 30% body surface area (BSA)
	
 Continue avelumab therapy per protocol. Symptomatic therapy (for example, antihistamines, topical steroids) 	
If persists > 1 to 2 weeks or recurs:
 
 withhold avelumab therapy Consider skin biopsy. 
 Consider 0.5 to 1.0 mg/kg/day methylprednisolone IV or oral equivalent. Once improving, taper steroids over at least 1 month, consider prophylactic antibiotics for opportunistic infections, and resume avelumab therapy following steroids taper. 
If worsens:
 
 Treat as Grade 3 to 4.

Grade 3 Covering > 30% BSA;
 
Grade 4 life threatening consequences
	
 Withhold avelumab for Grade 3 Permanently discontinue for Grade 4 or recurrent Grade 3. Consider skin biopsy. Dermatology consult. 1.0 to 2.0 mg/kg/day methylprednisolone IV or IV equivalent. Add prophylactic antibiotics for opportunistic infections. 	
If improves to Grade ≤ 1:
 
 Taper steroids over at least 1 month and add prophylactic antibiotics for opportunistic infections Resume avelumab therapy following steroids taper (for initial Grade 3).

MANAGEMENT of PULMONARY IMMUNE-RELATED ADVERSE EVENTS (irAEs)		
Pneumonitis	Management	Follow-Up

Grade 1 Radiographic changes only
	
 Consider withholding avelumab therapy. Monitor for symptoms every 2 to 3 days. Consider Pulmonary and Infectious Disease consults. 	
 Re-assess at least every 3 weeks. 
If worsens:
 
 Treat as Grade 2 or Grade 3 to 4.

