
Grade 1 or 2 endocrinopathies (hypothyroidism, hyperthyroidism, adrenal insufficiency, type I diabetes mellitus)
	
 • Continue avelumab therapy per protocol. • Endocrinology consult if needed 
 • Start thyroid hormone replacement therapy for hypothyroidism), anti-thyroid treatment (for hyperthyroidism), corticosteroids (for adrenal insufficiency) or insulin (for Type I diabetes mellitus) as appropriate. • Rule out secondary endocrinopathies (i.e. hypopituitarism/hypophysitis) 	
 • Continue hormone replacement/suppression and monitoring of endocrine functions as appropriate.

Grade 3 or Grade 4 Endocrinopathies (hypothyroidism, hyperthyroidism, adrenal insufficiency, Type I diabetes mellitus)
	
 • Withhold avelumab therapy • Consider hospitalization • Endocrinology consult • Start thyroid hormone replacement therapy (for hypothyroidism), anti-thyroid treatment (for hyperthyroidism), corticosteroids (for adrenal insufficiency), or insulin (for Type I diabetes mellitus) as appropriate • Rule-out secondary endocrinopathies (i.e. hypopituitarism / hypophysitis) 	
 • Resume avelumab once symptoms and/or laboratory tests improve to Grade ≤ 1 (with or without hormone replacement/suppression). • Continue hormone replacement/suppression and monitoring of endocrine function as appropriate.

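### Sections 11.2 and 11.6 set different conditions for resuming avelumab after a persisting Grade 2 immune-related rash and, more narrowly, after some severe endocrine events, and precedence between them is not settled

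*Combined protocol and SAP*

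**What the plan says.** Section 11.2 opens with its scope: "If a subject's avelumab treatment is held due to an adverse event that is possibly, probably or definitely related to avelumab". Its default is recovery to Grade 1 or less or to baseline, followed by exceptions. Two matter here:

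- Skin: "Subjects who have not experienced a Grade 3 drug-related skin AE may resume treatment in the presence of Grade 2 skin toxicity".
- Endocrine: "Drug-related endocrinopathies adequately controlled with only physiologic hormone replacement may resume treatment". No grade is attached to this exception.

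Section 11.6 has its own tables for immune-related events:

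- Rash, Grade 1-2: avelumab continues at first. The follow-up column then has a branch headed "If persists > 1 to 2 weeks or recurs", under which avelumab is withheld, a skin biopsy and steroids are to be considered, and the way back is: "Once improving, taper steroids over at least 1 month, consider prophylactic antibiotics for opportunistic infections, and resume avelumab therapy following steroids taper".
- The endocrine row for "Grade 1 or 2 endocrinopathies (hypothyroidism, hyperthyroidism, adrenal insufficiency, type I diabetes mellitus") continues avelumab.
- The Grade 3-4 endocrine row withholds, then: "Resume avelumab once symptoms and/or laboratory tests improve to Grade ≤ 1 (with or without hormone replacement/suppression").
- The hypophysitis row resumes at Grade 1 or less and, where the MRI was abnormal, also requires documented shrinkage of the pituitary.

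Three statements bear on precedence. The opening of 11.6 assigns events judged at least possibly immune-related to that section, unless the investigator considers another known standard more appropriate. Section 11.1 says that immune-related events of special interest are to be managed by local institutional practice. Section 11.2 contains no deferral to 11.6.

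**The concern.** An avelumab-related rash can also be judged immune-related, and it then falls under both 11.2 and 11.6. If the two give different conditions for the next dose, two investigators who follow the protocol can treat the same patient differently, and neither departs from the text.

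This is first a patient-safety matter, because one passage permits a dose that the other tells the investigator to withhold. It also touches the data. The safety profile is a co-primary objective (Section 3.1), and exposure, holds and discontinuations depend in part on which passage is followed.

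The stakes rise if steroids are used. Sections 11.1 and 11.2 require permanent discontinuation once the gap exceeds 28 days from the last dose, apart from cross-referenced exceptions. The steroid taper in the rash row lasts at least a month and starts only after improvement, so it would ordinarily run past that limit.

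**Working it through.** The point is textual and the plan states no figure to reproduce. The check applies both sections to specific patients.

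| Case | Section 11.2 | Section 11.6 | Conflict? |
|---|---|---|---|
| (a) Immune-related Grade 2 rash, beyond 2 weeks, not improving, no prior Grade 3 skin event | Resumption permitted | Withheld | Yes |
| (b) Grade 2 rash, improving, steroid taper completed, no prior Grade 3 skin event | Permitted | Permitted | No |
| (c) Drug-related skin event not judged immune-related | Permitted at Grade 2, if no prior Grade 3 | Does not apply | No |
| (d) Grade 1-2 endocrinopathy | Permitted if controlled | Treatment continues | No |
| (e) Grade 3-4 endocrinopathy, now Grade 1 or less on replacement | Permitted | Permitted | No |
| (f) Grade 3-4 endocrinopathy, controlled on physiologic replacement, still Grade 2 | Permitted | Not yet permitted | Yes, narrow |
| (g) Hypophysitis with abnormal MRI, controlled on replacement, no documented shrinkage | Permitted | Not permitted | Yes |

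Three of the seven cases conflict: (a), (f) and (g). In case (a) the 11.6 rash row does not ask for Grade 1 or less. It asks for improvement and, if steroids were given, a completed taper.

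**Precedence.** Section 11.6 claims immune-related events, with a discretion clause. Section 11.1 points immune-related events of special interest to local practice, and Section 14.5.12 counts any suspected immune-related event as one of special interest. Section 11.2 covers every avelumab-related event without exempting immune-related ones. Sections 11.2 and 14.5.12 also refer to a Section 11.7, but the contents end Section 11 at 11.6.

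**How many patients.** Section 4.5 reports rash and hypothyroidism each in at least 2% but under 5% of 717 treated subjects, at any grade. With 25 patients:

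- Expected per event: 25 × 0.02 = 0.5 to 25 × 0.05 = 1.25.
- Chance of at least one: 1 − 0.98^25 = 0.40 to 1 − 0.95^25 = 0.72.

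These figures count patients with any such event, not patients in cases (a), (f) or (g). The share of rashes that are immune-related, Grade 2 and persistent or recurrent is not given and could be anything from none to all, so the figures are only a loose ceiling for case (a).

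For case (f) they are far too high. Hypothyroidism is absent from Section 4.5's list of Grade 3 or higher related events seen in two or more subjects. If that list is complete (an assumption), there was at most 1 such event in 717. That gives 25 × 1/717 = 0.035 expected, and 1 − (716/717)^25, about 3%, for at least one. This covers hypothyroidism only; the documents do not allow the same sum for the other endocrinopathies.

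**Length of hold.** In the rash row steroids are to be considered, not required. The hold applies either way, but the minimum of a month follows only when steroids are given.

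**The case against.** The strongest reply is that 11.6 settles the overlap itself by claiming immune-related events in its opening statement, while 11.2 is only permissive. A site that follows the stricter 11.6 row breaches nothing in 11.2. The discretion clause also lets the investigator depart from 11.6.

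Much of this stands, and it rules out several stronger readings that a reader might infer:

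- That the same patient is both cleared and barred. Section 11.2 says a patient may resume and compels no dose, so the passages differ in what they allow rather than issuing opposite orders.
- That no section addresses which rule governs. The opening of 11.6 does.
- That the endocrine rules conflict throughout. Grade 1-2 events continue treatment, and the Grade 3-4 row expressly accepts recovery on hormone replacement, so only cases (f) and (g) differ.
- That 40% to 72% is the chance of meeting the conflict in this trial. It rests on any-grade rates.
- That each affected patient loses at least a month of dosing. Steroids are optional in the rash row.
- That the reported safety results will be distorted. The analysis is descriptive, with no comparative tests planned (Section 17.3), and no effect on a reported rate can be shown from the documents.

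The reply does not close the point. The scope statement in 11.6 competes with the local-practice sentence in 11.1 and with the unrestricted scope of 11.2. A permission in one section to give a dose that another says to withhold is still a contradiction for whoever must decide at the visit.

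**Conclusion.** The text is wrong as written and should be corrected. For an immune-related Grade 2 rash that persists without improving, with no Grade 3 drug-related skin event, 11.2 permits resumption and 11.6 withholds. A narrower mismatch exists for a Grade 3-4 endocrinopathy controlled on physiologic replacement but still above Grade 1, and for hypophysitis with an abnormal MRI and no documented shrinkage. The protocol leans towards 11.6 for immune-related events but does not settle the matter.

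The number of patients affected cannot be derived from the documents. The conclusion rests on the event being judged both avelumab-related and immune-related, which the protocol allows. It takes no position on which resumption rule is clinically right.

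**What to change.** Reconcile the skin and endocrine exceptions in 11.2 with the rash, Grade 3-4 endocrine and hypophysitis rows of 11.6. State in 11.1 and 11.2 which section governs an event that is both drug-related and immune-related, and bring the local-practice sentence in 11.1 into line with that statement. In the same amendment, correct the references to Section 11.7 and check the reconciled rash rule against the 28-day limit on delays.

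The choice of rule belongs to the sponsor's clinicians. The cost is one wording amendment with the usual approvals. It adds no procedures and does not change the sample size or the analysis.
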